3. DATA ANALYSIS CONSIDERATIONS

Overall analysis frame

This study is non-interventional and descriptive methods will be employed for data analyses. Descriptive analysis will be performed of all collected data, i.e. all data listed in section 2.3 ("Study variables"), except data collected only for the purpose of data cleaning. The primary and secondary outcomes of the study are presented in section 2.3.1 ("Efficacy variables").

Summary of study data

All continuous variables will be summarised using the following descriptive statistics: n (non-missing sample size), mean, standard deviation, median, 25 percentile, 75 percentile, maximum and minimum. The frequency and percentages (based on the non-missing sample size) of observed levels will be reported for all categorical measures. For variables marked "binary" exact (Clopper-Pearson) 95% confidence intervals will be calculated where appropriate. For categorical variables with more than 2 categories 95% confidence intervals will be calculated using Goodman's method or other appropriate (e.g. Sison and Glatz) method.

In general, all data will be listed, sorted by site and patient, and when appropriate by visit number within patient. All summary tables will be structured with a column for each cohort in the increasing order and will be annotated with the total population size relevant to that table/dose cohort, including any missing observations.

Baseline data

Baseline visit is a visit after physician makes a decision to prescribe Vipidia® for DM2T treatment. It means that investigator inform patient about the study only after taking decision about strategy of DM2T treatment.

Data to be collected:

- Date of visit (day, month, year)
- Date of Informed consent form signing (day, month, year)
- Compliance with Inclusion/exclusion criteria
- Demographic information: sex, date of birth, ethnicity, region of residence (city, town etc)

- Medical history and concurrent conditions: (condition, start/end date)
 - Nicotine use,
 - General medical history – body system, abnormality (ongoing or not at the study entry), date of diagnosis,
 - History of DM2T: - date of diagnosis of diabetes, historical complications of DM (diabetic retinopathy, autonomic neuropathy, diabetic nephropathy – and their date of diagnosis), family history of DM and cardiovascular diseases, previous DM2T treatment (including reason(s) for discontinuation of previous DM2T-treatment (if applicable));
 - History of cardiovascular and related disorders (arterial hypertension, IM, stroke, dyslipidaemia, arrhythmias, chronic heart failure, peripheral artery diseases, etc.)
- Physical examination and vital signs: height (cm), weight (kg), systolic and diastolic blood pressure (position, time, values), heart rate,
- Laboratory data (last available measurements, if done within routine practice):
 - Hb1Ac,
 - FPG,
 - PPG,
 - Lipid profile (total cholesterol, tryglycerides, low-density lipoproteins),
- The study medication:
 - prescribed Vipidia® dosage regimen;
- Concomitant treatment:
 - DM2T treatment - prescribed or current DM2T-treatment (if applicable),
 - Other concomitant treatment - INN, trade name, dosage regimen (dose taken), duration of treatment, indication for administration

All baseline data will be presented using denoted descriptive statistics (see chapter "Summary of study data") and conventional notations. The baseline visit is defined as the last observations collected prior to administration of the study drug.

4. CLINICAL DATABASE

Overall approach to data handling and recordkeeping described in the Protocol of the study.

The data from paper CRFs will be doubly entered into the common database by the authorized officers of CRO in accordance with the internal standard operational procedures. After completion of the entry process, computer logic checks will be run to identify items, such as inconsistent dates, missing data, and questionable values. Queries may be issued by the Sponsor and responsible CRO and will be answered by investigators.

The study database will be set up and maintained by responsible CRO in accordance with SOPs of responsible CRO.

The full details of procedures for data handling will be documented in the Data Management Plan.

Clinical Database Access Restrictions

Clinical Database Access Restrictions will be set in accordance with CRO's Standard Operational.

Database for final analysis

A snapshot of the clinical database will be generated after all subjects have completed through the final visit of the study or discontinued participation in the study. Snapshot for final analysis will be performed after database lock according to relevant CRO's Standard Operating Procedure (SOP) for database lock and data extraction. All tables, figures, and listings (TFLs) described in this SAP will be generated on this snapshot of the database.

Database for interim analysis

As soon as first 350 study patients have completed through final visit of the study or discontinue their participation a snapshot of the clinical database will be generated. The snapshot of the database will be performed in accordance with Standard operating procedures of CRO responsible for Data collection and data management. All tables, figures and listings described in this SAP will be generated on this interim snapshot of the database

5. STATISTICAL / ANALYTICAL ISSUES

Visit windows

In accordance with the protocol, due to the non-interventional study design it's not possible to appoint exact times for the study visits, although it is expected that the period of observation will be approximately 6 months. The frequency of the visits will be assigned by each physician according to their routine practice. It is anticipated that the patients will visit their physician every 3 months and more often at the beginning.

So, for the analysis and summary of clinical laboratory, efficacy, and safety data in case of this analysis/summary performed on "by visit" base. In the event of multiple values for an assessment within an analysis window, the value closest to the scheduled visit date will be used for analyses. If two values tie as closest to the time point (for example, one value is before and the other value is after the time point), then the later value will be selected as the analysis value.

Analysis Window	Start	End	Target	Assessment to be used if duplicates
Baseline visit	<1			NA
Month 3 (Visit 2)	0	135	90	Closest to target day, if equidistant use later result.
Month 6 (Visit 3)	136	NA	180	

The definition for the study days included in each study window is defined as below:

Treatment Day prior to first dose = Visit Date – Date of First Dose

Treatment Day on or after first dose = Visit Date – Date of First Dose + 1

Adjustments for Covariates

No specific adjustments for covariates will be made in all statistical analyses, unless specified otherwise per-analysis level.

Handling of Dropouts or Missing Data

Missing efficacy outcomes will be assumed to be missing at random (MAR) and thus will not be imputed in the primary analysis. However if greater than 1% of all primary/secondary outcomes that should be available for analysis are missing, a sensitivity analysis will be undertaken in addition to the primary MAR analysis.

This sensitivity analysis will include an evaluation of the results of models developed under the assumptions of:

- 1) last observation carried forward;
- 2) worst extreme case imputation and;
- 3) regression model imputation using all available information.

Outlier identification

During data Quality Control outlier identification will be performed using adjusted Z-score method (Iglewicz and Hoaglin, 1993).

$$M_i = \frac{0.6745(x_i - \bar{x})}{MAD}$$

where MAD - Median absolute deviation, \bar{x} - median.

Values with Z-score > 3.5 will be considered outliers for study variables considered normally distributed. Preliminary normality test (Shapiro–Wilk criterion) will be performed for these variables. In case if normality distribution hypothesis will be rejected based on Shapiro–Wilk test results, median and IQR (interquartile range) will be used for outlier identification. Values > 1.5 IQR far from median value will be considered outliers. No data will be excluded / modified based on outlier identification, however, additional medical context assessment for these data will be performed and data quality control / source verification check will be considered.

Interim Analyses

An interim analysis is planned to be performed as soon as first 350 patients have completed the study by achieving final study visit or discontinuing the study.

The reasons of performing this interim analysis is an importance of study data for medical society and commitment of the company to disclosure clinically relevant information to medical specialists.

At this level of the analysis study objectives listed in the sections 2.2.1-2.2.4 will be evaluated. The results will be provided according to reporting rules applicable for final statistical analysis and described in the Statistical Analysis Plan.

The interim analysis will be performed according to statistical procedures described in the sections # 05-10 of this Statistical Analysis Plan. No subgroup analyses are to be performed within interim analysis of the study.

The results of the interim analysis should be disclosed to public either through publication in medical scientific journal or within presentation at medical congress/conference.

After study is completed the complete study results are to be considered as prevailing the results of

interim analysis.

Multiple Comparisons/Multiplicity

When needed, corrections for multiplicity will be justified and performed according to Bonferroni. Overall alpha-level will be controlled and will not exceed 0.05. The interim analysis will not be taken into account within multiplicity adjustment procedure.

Examination of Subgroups

Some secondary endpoints will be analyzed in subgroups of patients with different clinical characteristics: demographic information, nicotine use, history of DM2T (see “EFFICACY ANALYSES” chapter).

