2. PROTOCOL SUMMARY

2.1 Study design and conduct

This is a local, prospective, multicentre, non-interventional, observational study in adult patients with T2DM diagnosis.

Due to the observational design, patient visits to the referring physician are not pre-specified by the study protocol, but will follow usual clinical practice. All patient-care decisions, including diagnostic and therapeutic interventions, will be made by and conducted at the discretion of the participating study physicians according to their clinical judgment and the local standard of medical care.

[figure not shown]
Start of the study is defined as the date of the start of data collection (first patient signed ICF for data collection).

End of the enrolment (Last Patient First Visit) is defined as the date when the last patient signs ICF and enrolled in the study.

End of the patient observation (Last Patient Last Visit) is defined as the last date when the patients are observed in the scope of the study.

End of study (end of data collection) is defined as the date when the last data point is collected. Up to this date all the CRFs should be completed and all the data clarifications (queries) should be done.

The study is considered to be completed after the database is closed, the final statistical analysis is performed and the study report is written. The study report must be signed within 12 months after the collection of the last data point.

It's planned that interim statistical analysis of study data will be performed as soon as 350 first study patients have completed the study by achieving final study visit or discontinuing their participation.

Term	Baseline visit (V1)	Observational visit (V2)	Final visit (V3)
Inclusion/exclusion criteria	X		
Signed Informed consent form	X		
Date of visit	X	X	X
Demographic information	X		
Medical history including history of DM2T	X		
Concurrent medical conditions	X		
Physical examination and vital signs*	X	X	X
Study medication	X	X	X
Laboratory tests and instrumental exams*	X	X	X
Concomitant treatment (including DM2T treatment)	X	X	X
Healthcare resources utilization		X	X
Adverse events		X	X

For study details and study assessment's schedule see the Protocol of the Study.

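### The Baseline and Month 3 windows do not fit the SAP's own day formulas: a value dated on the first-dose date leaves Baseline and enters Month 3, contrary to the SAP's definition of baseline

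*SAP*

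**What the plan says.** SAP section 5 (Visit windows) gives three windows in treatment days: Baseline below 1; Month 3 (Visit 2) from 0 to 135, target 90; Month 6 (Visit 3) from 136 with no upper limit, target 180. Days are counted by two formulas: "Treatment Day prior to first dose = Visit Date – Date of First Dose" and "Treatment Day on or after first dose = Visit Date – Date of First Dose + 1". Choosing the value closest to target applies "In the event of multiple values for an assessment within an analysis window"; a lone value is used as it stands.

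Section 3 (Baseline data) defines baseline separately: "The baseline visit is defined as the last observations collected prior to administration of the study drug". It also says "Baseline visit is a visit after physician makes a decision to prescribe Vipidia® for DM2T treatment", and for laboratory data it takes the latest routine measurements available, which need not have been made on the day of V1. Among the baseline items, section 3 lists a time of measurement only for blood pressure.

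The SAP does not say whether the section 3 definition or the section 5 table prevails when they differ.

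**The concern.** As printed, the two windows overlap at Day 0, and under the formulas the boundary falls in the wrong place. V1 follows the decision to prescribe, so some patients may take their first dose on the V1 date. For them the table removes the V1 value from Baseline and offers it to Month 3, while section 3 makes it the baseline. Two programmers who each follow the SAP could derive different data for the same patient.

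Baseline enters every change endpoint. V2 values enter the V1-V2-V3 changes, the proportion with an HbA1c decrease of at least 0.3%, the V2 marked-hyperglycemia proportion and the repeated-measures model in section 9.1. A pre-treatment value used as V2 gives a change of zero by construction.

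**Working it through.** **Day mapping.** Let d = visit date minus date of first dose. By calendar date, the treatment day is d if d < 0 and d + 1 if d ≥ 0.

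| d | Treatment day | Window in the SAP table |
|---|---|---|
| -1 | -1 | Baseline |
| 0 | 1 | Month 3 only |
| 6 | 7 | Month 3 |
| 29 | 30 | Month 3 |
| 134 | 135 | Month 3 |
| 135 | 136 | Month 6 |

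No d gives Day 0, so the printed start of Month 3 is a day that never occurs. The first day that actually enters Month 3 is Day 1, the first-dose date.

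**Selection within Month 3** (closest to 90, the later value if tied). Values on Days 1 and 85: Day 85 is chosen. Days 1 and 8: Day 8. Day 1 alone: Day 1. Days 1 and 179: Day 1 becomes Month 3 and Day 179 becomes Month 6. The rule therefore protects only patients with another value by Day 135.

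**If the table overrides section 3: effect on the primary endpoint.** Inputs from section 2.4: SD 0.70, correlation 0.35, target half-width 0.05, 1037 pairs required, 1052 evaluable patients planned.

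- SD of change = 0.70 × √(2 × (1 − 0.35)) = 0.798.
- Check on the SAP: the probability that the half-width is at most 0.05 at n = 1037 comes to 0.901, against 0.900 printed.
- Margin: 1052 − 1037 = 15 patients, or 15/1052 = 1.4%.
- Expected half-width = t(0.975, n−1) × 0.798/√n.

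| Assumed share without a baseline | n left of 1052 | Expected half-width |
|---|---|---|
| 0% | 1052 | 0.0483 |
| 2% | 1031 | 0.0488 |
| 5% | 999 | 0.0496 |
| 10% | 947 | 0.0509 |
| 20% | 842 | 0.0540 |

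A 2% loss already takes n below the 1037 needed for 90% assurance. The expected half-width passes 0.05 only at about n = 981, a loss of 71/1052 = 6.7%.

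**If section 3 governs: effect on V2.** Let p be the share of V2 values that are reused V1 values.

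- Mean V2 change becomes (1 − p) × the true change. For p = 2, 5 or 10% it shrinks by 2, 5 or 10%.
- Proportion with an HbA1c decrease of at least 0.3%: an assumed 60% becomes (1 − p) × 60% = 58.8, 57.0 or 54.0%.
- Marked hyperglycemia: take an assumed 5% on treatment and an assumed 20% before treatment. Then (1 − p) × 5% + p × 20% = 5.3, 5.75 or 6.5%. With 10% before treatment the results are 5.1, 5.25 or 5.5%; with 30% they are 5.5, 6.25 or 7.5%.

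The shares lost, p, the 60%, the 5% and the pre-treatment 10 to 30% are all assumptions; the SAP gives none of them.

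**The case against.** The best defence is that the SAP already says what baseline is. Section 3 defines it as the last pre-dose observation, the schedule in section 2.1 labels V1 the baseline visit, and the Month 3 window is labelled Visit 2. A sensible programmer would not file a V1 record as Visit 2. This carries weight, and it makes the worst outcomes less likely. But the SAP gives no order of precedence, and neither the definition nor the labels exclude the value from a window defined by days.

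Second, same-day dosing is inferred. Section 3 records a prescribed regimen at V1, not a dose taken, and section 7 defines prior medications as those taken between consent and first dose, which allows for an interval. If dosing starts the next day, V1 is Day -1 and nothing goes wrong. Third, baseline HbA1c and fasting glucose may have been sampled before V1; if the sampling date is used they stay in Baseline. The formula, however, refers to the visit date. Both points stand as limits on frequency.

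A reader might also infer more than the text supports:

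- *That a same-day value lies in both windows.* This requires reading the pre-dose formula by clock time. The formulas use dates only, and the literal result is Month 3 only.
- *That the wide Month 3 window is itself an error.* Section 5 says that "It is anticipated that the patients will visit their physician every 3 months and more often at the beginning", so lone early values can occur, and one on Day 7, 14 or 30 reflects 8, 16 or 33% of the 90 target days. But a wide, contiguous window is defensible where visit times cannot be fixed, and a lower limit would discard some patients' only V2 value.
- *That a Month 1 window is missing.* The Month 1 row in mock Table 2 is generic layout; mock Table 5 lists months 0 to 6 although the study has three visits.

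**Conclusion.** The boundary error is certain: the table and the formulas disagree, and a value dated on the first-dose date is assigned contrary to section 3. The consequences are conditional and of unknown frequency.

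Reuse of a V1 value at V2 needs first dosing on the V1 date, no other value by Day 135 and, for laboratory values, dating by visit rather than by sampling. Loss of the primary V3 change needs the table to override section 3 and no earlier-dated value to be usable. A reader might conclude that the primary analysis is in serious danger. The documents do not support that: on the SAP's own worst-case SD, losing 5% of baselines would move the expected half-width from 0.0483 to 0.0496, still under 0.05, and a 10% loss would take it to 0.0509. The correction is worth making because it is specific, nearly free, and concerns the derivation that every change endpoint uses.

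**What to change.** In section 5:

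1. State that the section 3 definition of baseline governs.
2. Define Baseline as the last value on or before Day 1, with V1 values dated Day 1 treated as pre-dose unless recorded otherwise. This needs no clock times.
3. Start Month 3 at Day 2.
4. Bar any value used as baseline from Month 3.

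This costs only SAP wording and a change to the window derivation. It needs no new data and removes no V3 value. A patient whose only value up to Day 135 is the baseline value would have no V2 result, which is correct.

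Optionally, report V2 efficacy results with and without very early lone values, for example those before Day 45 (90 − 45, mirroring the stated upper limit of 90 + 45 = 135), while keeping them in the main summary. The cost is one extra set of tables.

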9.1. Statistical Analysis of the Primary Efficacy Variable(s)

Primary study outcome - change from baseline in glycosylated hemoglobin (HbA1c) level on Vipidia® therapy (V3). Taking into account inclusion criteria (either newly diagnosed DM type 2 (drug naive) or inadequate glycemic control on previously prescribed any oral antidiabetic drug) as well as non-intervention nature of the study it is proposed to use multifactorial regression model to determine factors related to effect of Vipidia® on glycosylated hemoglobin (HbA1c) level dynamics.

Change from baseline in glycosylated hemoglobin (HbA1c) level on Vipidia® therapy (V3) in subgroups with different clinical characteristics will be summarized using relevant descriptive statistics and analyzed using Multiple Linear Regression with following predictors: prior therapy of DM, sex, age, cardiovascular risk group, therapy type (monotherapy or combined therapy), baseline BMI, initial glycemic control, T2DM duration. No subgroup analyses will be performed within interim analysis of study data.

In addition, change from baseline in glycosylated hemoglobin (HbA1c) level will be assessed and evaluated using Mixed model repeated measures (MMRM) methodology [14, 15]. The multiple visits for each patient will be incorporated as repeated measures within each patient. Visit will be treated as a categorical predictor and baseline glycosylated hemoglobin (HbA1c) level and duration of T2 DM will be included as a covariate. An appropriate covariance structure will be selected to provide estimates (Least Square Means) of change from Baseline and to perform statistical analysis at Visit 3. The dose-response trend hypothesis test will be conducted using the appropriate contrast statement for a linear (ordinal dose) trend. In addition, Least Squares Means, the associated standard errors and 95% confidence intervals will be displayed by each individual dose group.

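### No visible HbA1c analysis allows for clustering by site, so the 95% intervals are likely too narrow by an amount the SAP does not let one determine

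*SAP*

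**What the plan says.** Section 2.1 sets the design: "This is a local, prospective, multicentre, non-interventional, observational study in adult patients with T2DM diagnosis". Under the same heading, "All patient-care decisions, including diagnostic and therapeutic interventions, will be made by and conducted at the discretion of the participating study physicians". Section 5 (Visit windows) adds: "The frequency of the visits will be assigned by each physician according to their routine practice". For baseline, section 3 takes "Laboratory data (last available measurements, if done within routine practice", a list that includes HbA1c.

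The analyses are these:

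- **Regression of HbA1c change at V3 (section 9.1).** Eight patient-level predictors: "prior therapy of DM, sex, age, cardiovascular risk group, therapy type (monotherapy or combined therapy), baseline BMI, initial glycemic control, T2DM duration". Site is not one of them.
- **MMRM (section 9.1).** Visit, baseline HbA1c and diabetes duration, plus a dose-trend contrast. On correlation: "The multiple visits for each patient will be incorporated as repeated measures within each patient". No level above the patient is mentioned.
- **Secondary mixed models (section 9.2).** The independent factors are clinical characteristics, not listed further.
- **Additional tests (end of section 9.2).** Paired t or Wilcoxon.
- **Precision calculation (section 2.4).** Independent pairs, with no design effect.

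Section 5 (Adjustments for Covariates) gives the general rule: "No specific adjustments for covariates will be made in all statistical analyses, unless specified otherwise per-analysis level". In the analysis text, site serves only as a sort key for listings (section 3, Summary of study data).

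**The concern.** Patients of one site share a physician's prescribing habits, visit pattern and probably a laboratory. Their HbA1c changes may therefore resemble each other more than those of patients at different sites. A randomised comparison within sites would cancel much of this. Here there is one arm and the target is a mean change, so nothing cancels, and between-site variance adds in full to the variance of the estimate.

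This matters because section 2.4 sizes the primary objective on the width of a confidence interval, with no hypothesis test. If that interval leaves out a source of variance, it covers less often than its label says. The same methods apply to the interim analysis of the first 350 patients, whose results are to be made public (section 5, Interim Analyses).

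A second, smaller issue is confounding. Therapy type is a regression predictor and dose enters the MMRM trend test. Both can follow local prescribing habits, so without site in the model, differences between sites could be read as effects of therapy type or dose.

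**Working it through.** **Inputs from SAP section 2.4:** SD 0.70, within-pair correlation 0.35, two-sided alpha 0.05, probability of achieving the width 0.9, half-width 0.05 (tightest row), 1037 pairs, dropout 25%.

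**Step 1. Reproduce the plan's figure.**
- SD of the paired difference = 0.70 × √(2 × (1 − 0.35)) = 0.798.
- The smallest n for which t × s/√n ≤ 0.05 has probability at least 0.90, given that the interval covers, is 1037 (probability 0.9002; the SAP shows 0.900). The rows for 770, 899, 275 and 206 pairs also reproduce.
- Enrolment: 1037/0.75 = 1383, as stated.

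The calculation is correct for independent patients.

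**Step 2. Expected half-width under independence.** 1.96 × 0.798/√1037 = 0.0486.

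**Step 3. Add clustering.** With m patients per site (equal sites) and between-site ICC:
- design effect DE = 1 + (m − 1) × ICC
- true half-width = 0.0486 × √DE
- real coverage of the unadjusted 95% interval = 2Φ(1.96/√DE) − 1

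The SAP states neither m nor ICC, so the first two columns are assumptions.

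| ICC | m | DE | Half-width at 1037 pairs | Coverage |
|---|---|---|---|---|
| 0 | any | 1.00 | 0.049 | 95% |
| 0.01 | 10 | 1.09 | 0.051 | 94.0% |
| 0.02 | 20 | 1.38 | 0.057 | 90.5% |
| 0.05 | 20 | 1.95 | 0.068 | 84.0% |
| 0.05 | 50 | 3.45 | 0.090 | 70.9% |

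**Step 4. Compare with the precision target.** Section 2.4 asks for a half-width between 0.05 and 0.1. The expected half-width passes 0.05 once DE exceeds (0.05/0.0486)² ≈ 1.06. It passes 0.1 only once DE exceeds (0.1/0.0486)² ≈ 4.2. Every row of the table lies below that upper limit.

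**The case against.** **The size is unknown.** The SAP gives no ICC, number of sites or patients per site, so every clustered figure is assumed, and the range runs from trivial to large. This stands. A reader might infer that the intervals are certain to be too narrow. The document does not show that: it requires a positive ICC for HbA1c change and inference beyond the participating sites.

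**The sample size has not failed.** 1037 pairs is the tightest corner of an 18-row table, and the target reaches 0.1. This also stands. In addition, 0.70 is described as applying to HbA1c dynamics and could be read as the SD of change itself. The half-width at 1037 pairs would then be 1.96 × 0.70/√1037 = 0.043, and a design effect of 1.38 would still give about 0.05. That affects width only; the coverage column depends on DE alone.

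**Section 5 forbids nothing.** Its rule concerns covariates and allows exceptions by analysis, and section 9.1 uses that allowance. A reader might take it as a bar on site adjustment, which it is not. The firmer ground is the MMRM sentence in 9.1, which places correlation within the patient only.

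**The evidence has limits.** The routine-practice wording in section 3 covers baseline laboratory data only. Dose is in the MMRM trend test, not in the regression. Prior therapy was prescribed earlier, and nothing shows that the study physician chose it. Much of the exploratory material in 9.2 and 9.3 is redacted, so the statement covers visible analyses only.

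**The study is descriptive, and this is an omission.** Section 3 does call the methods descriptive, and nothing in the SAP is contradicted. But the SAP specifies its models and reports 95% intervals, and an interval needs a valid standard error whatever the label. Site counts may properly sit in the protocol; the structure of the models belongs in the SAP.

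**Conclusion.** The point holds as a cheap improvement. Followed as written, the plan yields an interval for mean HbA1c change that leaves out between-site variance. The features described in section 2.1 and under Visit windows make some positive ICC plausible, so the interval is likely too narrow. Across the first three clustered cases in the table, coverage would be about 94% to 84% instead of 95%; the 50-per-site row shows that larger sites would make it worse. These values assume equal site sizes and inference to sites beyond those taking part.

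The consequence is understated uncertainty. Planned precision is not shown to fail, and no increase in enrolment follows from this point.

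**What to change.** 1. In sections 9.1 and 9.2, add a random intercept for site to the regression and mixed models, or use site-clustered robust standard errors.
2. Report the mean change in HbA1c at V3 with a site-clustered 95% interval.
3. Report the between-site variance or ICC of HbA1c change with the primary result, so that readers can see whether clustering mattered.
4. In section 5 (Adjustments for Covariates), name site as a per-analysis exception.
5. Apply the same to the interim analysis.

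A random intercept only partly removes confounding by site of therapy type and dose, and the report should say so when interpreting those effects.

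The cost is SAP wording and one extra model term. Site is already available, since listings are sorted by it, so no new data are needed. The reported interval may be somewhat wider; if the ICC is near zero it will barely move.
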